6.6. Cervical Length

As routine practice, some institutions may measure cervical length by transvaginal ultrasound as an indicator of risk of delivery within hours to days. For these institutions already routinely performing this measurement, the cervical length data will not be used to determine eligibility but should be recorded in the eCRF. The data will not be used to determine eligibility but should be recorded for use in an exploratory analysis of cervical length as a marker of preterm labor and response to treatment. Additional details are provided in the SPM.

6.7. Fetal Fibronectin

Institutions that routinely perform fFN testing should record the result in the eCRF. Results will not be used to determine subject eligibility but will be used in an exploratory analysis of fFN as a marker of preterm labor and response to treatment. Details for sample collection and processing are in the SPM.

6.8. Biomarkers

A biomarker is a molecule associated specifically with a disease or condition such that it allows for the diagnosis, risk identification, or optimization of treatment. A maternal blood sample for biomarker research will be collected at Screening and a cord blood sample for biomarker research will be collected during the Delivery Phase. The samples will be stored and may be analyzed for future exploratory research.

The blood samples collected for biomarker analyses are summarized further in [Appendix 5](#).

6.9. Genetic Research

Pharmacogenetics is the study of how drug response varies in individuals due to genetic differences. Genetic differences also may contribute to preterm labor risk and progression. At Screening (Day 0), a 6-mL blood sample for maternal DNA will be collected in subjects who provide informed consent for genetic research. In addition, for

those subjects who deliver at the investigative center, a cord blood sample will also be collected for potential genetic assays.

Additional information regarding genetic research is included in [Appendix 1](#) and [Appendix 5](#).

7. DATA MANAGEMENT

For this study subject data will be entered into GSK/PPD-defined eCRFs, transmitted electronically to GSK/PPD or designee and combined with data provided from other sources in a validated data system.

Management of clinical data will be performed in accordance with applicable GSK/PPD standards and data cleaning procedures to ensure the integrity of the data, e.g., removing errors and inconsistencies in the data. Adverse events and concomitant medications terms will be coded using the MedDRA and an internal validated medication dictionary, GSKDrug.

Electronic CRFs (including queries and audit trails) will be retained by GSK, and copies will be sent to the investigator to maintain as the investigator copy. In all cases, subject initials will not be collected or transmitted to GSK according to GSK policy.

8. DATA ANALYSIS AND STATISTICAL CONSIDERATIONS

8.1. Hypotheses

The primary endpoint is prolongation of pregnancy as measured by time to delivery (days). The following are the null (H_0) and alternative (H_1) hypotheses for the primary endpoint in this study:

- H_0 : The prolongation of pregnancy as measured by time to delivery is equal between the women randomized to retosiban versus atosiban
- H_1 : The prolongation of pregnancy as measured by time to delivery is unequal between the women randomized to retosiban versus atosiban

The hypotheses will be tested at 5% level with a 2-sided test. To preserve the overall type I error rate, the key secondary analysis will be performed if and only if the null hypothesis of the primary endpoint is rejected. In addition, a sequential testing method will be used to adjust for multiplicity of key secondary endpoints such that the type I error rate will be maintained at 5%. Refer to Section [8.3.5.1.2](#) for details of key secondary analysis.

8.2. Study Design Considerations

8.2.1. Sample Size Assumptions

A total of 330 women (165 women per treatment group) will be recruited into the study and randomly assigned to treatment to ensure that 300 women/newborns (150 women/newborns per treatment group, assuming 10% missing data) have recorded

birth data, which provides 86% statistical power to detect an average difference of 9.5 days between retosiban and atosiban in time to delivery in the proposed adaptive design with futility analysis.

The above sample size calculations are based on a 2-sided testing procedure with a type I error rate of 5% and an approximate 10% dropout rate. Calculations are based on simulations and assumes that the percentage of women enrolled into each of the GA strata $24^{0/7}$ to $25^{6/7}$, $26^{0/7}$ to $27^{6/7}$, $28^{0/7}$ to $30^{6/7}$, and $31^{0/7}$ to $33^{6/7}$ will be 7%, 13%, 27%, and 53% (1:2:4:8 ratio), respectively, and approximately 55% of women in the atosiban treatment group will deliver within the 3 weeks of GA at randomization. The details of the model assumption and simulation are included in a supplemental simulation report.

Statistical Operating Characteristics

Simulations were carried out to determine the statistical properties for inference about the primary hypothesis of the adaptive design with regard to the control of the overall type I error and the statistical power under a wide range of efficacy for retosiban, from no effect (i.e., null hypotheses) to an increase of 9.5 days in time to delivery (i.e., alternative hypothesis) and to greater than expected efficacy. It was shown that the overall type I error rate (2.4%) was maintained at a level well below the 5% for the primary hypothesis. Furthermore, if the true effect of retosiban is small or zero, there is good probability (74%) that the study will be stopped early for lack of efficacy (i.e., futility). If the true effect of retosiban is as expected, the statistical power will be 86%, with a 7% probability that the study will be stopped for lack of efficacy. The details of model assumption and simulation are included in a supplemental simulation report.

Table 7 Operating Characteristics of the Adaptive Design Under the Null and Alternative Hypotheses

Case Hypothesis	Interim Analysis		Final	
	Futility	Failure	Failure	Success
Null (0 day)	74%	24%		2.4%
Alternative (9.5 days)	7%	7%		86%

8.2.2. Sample Size Sensitivity

It is expected that the time to delivery will be dependent on the percentage of women enrolled into each of the GA strata and the percentage of women that deliver within 3 weeks of randomization. Subsequently, the power of the study is expected to be sensitive to the assumptions used to determine the study sample size.

Further work has been done by GSK (details on file with GSK) to evaluate the sensitivity of the power of the study if the assumptions do not hold. In those analyses, the power of the study was most sensitive to assumptions regarding the percentage of women that delivered within 3 weeks of randomization. If the proportion of women delivering within 3 weeks is 45%, 10% lower than expected, the power of the study will be approximately 75% to detect an average difference of 7.7 days between retosiban and atosiban in the time to delivery. If it is significantly lower, such as 20% lower, the power of the study

could be as low as 53% to detect an average difference of 5.8 days between retosiban and atosiban in the time to delivery. Details will be included in a supplemental simulation report.

8.2.3. Sample Size Re-estimation

Sample size re-estimation is not planned for this study.

8.3. Data Analysis Considerations

8.3.1. Analysis Populations (Maternal)

8.3.1.1. Maternal Safety Population

The Maternal Safety Population is defined as all subjects randomly assigned to treatment that have been exposed to study treatment. Randomly assigned subjects will only be excluded if there is clear evidence the subject did not receive IP. Subjects will be analyzed according to their actual treatment in case this differs from their randomized treatment. This will be the primary population for assessing maternal and fetal safety.

8.3.1.2. Maternal ITT Population

The Maternal ITT Population, also known as the full analysis set, comprises all randomly assigned subjects who have been exposed to study treatment irrespective of their compliance to the planned course of treatment. Subjects who are randomly assigned but fail to receive any study treatment (as described in Section 4.4.1.1) will be excluded from the ITT Population. This is the primary analysis data set and will be used for evaluation of all maternal and fetal efficacy endpoints.

8.3.1.3. Maternal Per-Protocol Population

This Maternal Per-Protocol Population is defined as all subjects in the Maternal ITT Population excluding those who are major protocol violators. Subjects will be analyzed according to their actual treatment in case this differs from their randomly assigned treatment. This will include exclusions for use of prohibited concomitant medications and failure to meet inclusion criteria specified by the protocol.

8.3.2. Analysis Population (Neonatal)

8.3.2.1. Neonatal Safety Population

The Neonatal Safety Population is defined as neonates whose mothers received randomized treatment. The neonates will be analyzed according to the actual treatment the mother received in case this differs from randomized treatment. This will be the primary population for assessing neonatal safety.

8.3.2.2. Neonatal ITT Population

The Neonatal ITT Population, also known as the full analysis set, comprises all neonates of mothers who were randomly assigned subjects exposed to study treatment irrespective

of their compliance to the planned course of treatment. This is the primary analysis data set and will be used for evaluation of all neonatal efficacy endpoints.

8.3.2.3. Neonatal Per-Protocol Population

This Neonatal Per-Protocol Population is defined as all subjects in the Neonatal ITT Population excluding those who are major protocol violators.

8.3.3. Treatment Comparisons

8.3.3.1. Primary Comparisons of Interest

The primary comparison of interest is retosiban versus atosiban for time to delivery based on the ITT population, at the 2-sided 5% level.

8.3.3.2. Other Comparisons of Interest

For each of the secondary endpoints, the comparison of interest is retosiban versus atosiban at the 2-sided 5% level. Other comparisons of exploratory endpoints between retosiban and atosiban will be discussed in the RAP.

8.3.3.3. Subgroup Analysis

Additionally, comparisons of retosiban versus atosiban for primary and key secondary endpoints may also be performed for the following subgroups:

- GA strata $24^{0/7}$ to $25^{6/7}$, $26^{0/7}$ to $27^{6/7}$, $28^{0/7}$ to $30^{6/7}$, or $31^{0/7}$ to $33^{6/7}$
- Established progesterone use (yes or no)

Other potential subgroup comparisons will be described in the RAP.

8.3.3.4. Exploratory Covariate Analyses

Other exploratory covariate analyses will be performed to examine the relationship between the treatment response and potential covariates including baseline fFN value, subclinical intrauterine infection, other concomitant medications, etc. Details of analysis will be included in final RAP.

8.3.4. Interim Analysis

To ensure mother and infant safety, an IDMC will be used to periodically monitor the benefit:risk profile of subjects in the study. Safety and efficacy summaries will be provided to the IDMC by an independent statistical data analysis center. The IDMC will review periodic data to monitor potential benefit:risk profiles of the study intervention. With considerations for safety, recommendations may be made to modify the protocol or discontinue the study if any untoward events or pattern of events are detected.

There will be single planned interim analysis when approximately 130 subjects (65 subjects per treatment group) have completed delivery and have time-to-delivery results available. The primary objective of the interim analysis will be to determine if the

study will be terminated for lack of efficacy (futility) based on prespecified criteria. The decision will be based primarily on the analysis of the primary endpoint, time to delivery; however, all available safety and efficacy data will be reviewed.

Time to delivery will be analyzed as described in Section 8.3.5.1.1. An estimate of the difference in time to delivery between the retosiban and atosiban treatment group will be computed. Additionally, the conditional power of rejecting the null hypothesis at the end of the study based on the observed difference will be computed.

Full details of the statistical analysis and prespecified decision rules will be provided. The responsibilities of the IDMC and statistical data analysis center, as well as full details of the specific summaries and analyses of safety and efficacy data to be reviewed (including tables, listings, and summaries) will be provided in either the IDMC charter or the specific RAP for the IDMC.

8.3.5. Key Elements of Analysis Plan

8.3.5.1. Efficacy Analyses

8.3.5.1.1. Primary Analysis

The primary objective of the statistical analysis will be to test the null hypothesis in the ITT population that there is no difference between retosiban and atosiban in time to delivery versus the alternative hypothesis that there is a difference.

The primary analysis of time to delivery will utilize a finite mixture model [McLachlan, 2000] with 2 components, 1 for those women that delivery imminently and the other for the women delivering at term. The exact weight of each component will be determined by the observations from the component and model concomitant variables including treatment and GA at randomization. Within each component, the expected time to delivery will be modeled as a function of treatment as fixed effect and GA at randomization and established progesterone use (yes or no) as a covariate. The model parameters will be estimated using expectation-maximization algorithm. Point estimates, associated 95% CIs, and p-values for the overall average difference in time to delivery between retosiban and atosiban will be derived using the weighted average of model parameter estimates and variance from each subpopulation of mixture model. Details of mathematical model and analysis will be included in the RAP.

8.3.5.1.2. Secondary Analysis

Key Secondary Analysis

The key secondary analysis for this study includes the proportion of births prior to $37^{0/7}$ weeks' gestation, proportion of births at term ($37^{0/7}$ to $41^{6/7}$ weeks' gestation), length of neonatal hospital stay, and composite neonatal morbidity and mortality. To preserve the overall type I error rate, the key secondary analysis will be performed if and only if the null hypothesis of the primary endpoint is rejected. In addition, a sequential testing method will be used to adjust for multiplicity of the key secondary endpoints such that the type I error rate will be maintained at 5%. The sequential testing examines the

hypothesis testing in a prespecified order, i.e., the testing of the second secondary endpoint will be performed only if the first secondary endpoint is significant at 5%, and testing of the third secondary endpoint will be performed only if the first and second endpoints are significant at 5%. The exact order of sequential testing will be detailed in the RAP.

For the endpoints of neonatal composite outcome, proportion of births prior to $37^{0/7}$ weeks' gestation, and proportion of births at term ($37^{0/7}$ to $41^{6/7}$ weeks' gestation), a logistic regression model will be used for comparing retosiban with atosiban, with GA at randomization and established progesterone use (yes or no) as a covariate. The model will use a logit link function to estimate the log odds of percentage of preterm birth. The model will include terms for treatment group, established progesterone use, and GA at randomization. The number and percentage of subjects in each treatment group, the odds ratio of response rates (retosiban versus atosiban), 95% CIs for the odds ratio of response rates, and p-value will be presented. The relative risk response rates will be computed from the odds ratio.

Length of hospital stay will be log-transformed prior to analysis. Log-transformed length of hospital stay will be analyzed using an analysis of covariance adjusting for the covariate of GA at randomization and established progesterone use (yes or no). Other covariates may be added at discretion of the study statistician. The model-adjusted length of stay will be presented for each treatment group. In addition, the treatment difference between retosiban and atosiban and associated CIs and p-values will be presented.

The Wilcoxon rank sum test will also be performed for length of hospital stay if the assumption of normality is violated after log transformation.

Additionally, interactions between GA at randomization and treatment and established progesterone use and treatment will also be investigated.

Other Secondary and Exploratory Analysis

Binary secondary analysis endpoints will be analyzed in a similar fashion to the neonatal composite analysis. Binary exploratory endpoints will be analyzed in a similar fashion to the key secondary endpoints. The details of analysis will be provided in the RAP.

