4.2. Inclusion Criteria

Specific information regarding warnings, precautions, contraindications, AEs, and other pertinent information on the GSK IP or other study treatment that may impact subject eligibility is provided in the IB [GlaxoSmithKline Document Number CM2006/00201/05], the package insert for atosiban [Tractocile SmPC, 2013], and other pertinent documents.

Deviations from inclusion criteria are not allowed because they can potentially jeopardize the scientific integrity of the study, regulatory acceptability, or subject safety. Therefore, adherence to the criteria as specified in the protocol is essential.

Subjects eligible for enrollment in the study must meet all of the following criteria:

1. Signed and dated written informed consent is required prior to a subject's participation in Study 200721 (ZINN) and the performance of any protocol-specific procedures. At sites where enrollment of adolescents is allowed, adolescents aged 12 to 17 years must provide written agreement to participate in the study in accordance with applicable regulatory and country or state requirements. Subjects will also be asked to sign a release for medical records at the time of consenting to allow access to both the maternal and neonatal records including information about delivery and infant care as well as information collected prior to the consent having been signed.

Note: Prescreening alone does not necessarily require consent as this activity may be accomplished in the absence of study-specific procedures or assessments. In many cases, standard care and standard medical triage will provide sufficient information or evidence as to whether or not the subject is eligible for the study.

2. Females aged 12 to 45 years, with an uncomplicated, singleton pregnancy and intact membranes in spontaneous preterm labor (Note: This protocol includes pregnant adolescents, aged 12 to 17 years, as appropriate, unless national or local regulations restrict the age for study enrollment to subjects aged 18 to 45 years.)
3. Gestational age between $24^{0/7}$ and $33^{6/7}$ weeks as determined by (1) known fertilization date, either *in vitro* fertilization or intrauterine insemination or (2) a best estimated due date confirmed or established by the earliest ultrasound performed prior to $24^{0/7}$ weeks' gestation

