
 For binary endpoints, the number and percentage of subjects in each treatment group, the relative risk (RR) and 95% CIs, the odds ratio (OR) of response rates (retosiban versus atosiban) and 95% CIs, and p-value will be presented. The model-adjusted length of stay will be presented for each treatment group. In addition, the treatment difference between retosiban and atosiban and associated 95% CIs and p-values will be presented. Observed values using descriptive statistics for length of stay will be presented for each treatment group. For proportion of neonates with any of the composite component, neonates with any of the composite component w/o RDS, neonates with any of the composite component w/o RDS and mortality, and individual composite component, RR and 95% CIs, OR and 95% CIs, and p-values will be provided. 	
Sensitivity and Support Statistical Analysis	

 For length of stay, data will be analyzed in a similar fashion as described in Section 7.1.2. 	

Key Secondary Efficacy Statistical Analysis

- Treatment effects within defined subgroups in Section 5.1 will be explored.

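### The relative risk is to be derived from a covariate-adjusted odds ratio by an unstated method; the usual conversion would push it away from 1 by an amount that depends on covariate strength

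*Protocol*

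**What the plan says.** Protocol 8.3.5.1.2 specifies logistic regression for births before 37 weeks, births at term and the neonatal composite: "The model will include terms for treatment group, established progesterone use, and GA at randomization". From that model it reports counts and percentages, the odds ratio, "95% CIs for the odds ratio of response rates, and p-value will be presented". The next sentence is "The relative risk response rates will be computed from the odds ratio". It names no formula, no baseline risk and no interval for the RR.

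SAP 8.1.2 keeps the model and lists, for binary endpoints, "the relative risk (RR) and 95% CIs, the odds ratio (OR) of response rates (retosiban versus atosiban) and 95% CIs", plus a p-value. It neither repeats the conversion nor replaces it. SAP 8.1.3 carries the approach to the other binary endpoints, and SAP 8.2.4.1 asks for an RR with CI for ICU or NICU admission. The worked code in SAP 11.7.2 for the multiply imputed composite pools log odds ratios only. The list of changes in SAP section 9 does not mention the RR.

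**The concern.** The only odds ratio described in either document is adjusted for GA and progesterone use. The odds ratio is non-collapsible: when a covariate predicts the outcome, the conditional odds ratio lies further from 1 than the marginal one, even with perfect balance between arms. The common conversion combines an odds ratio with the control-arm risk. It returns the marginal RR only if it is fed the marginal odds ratio. Feeding it the conditional one together with the crude control risk mixes two scales.

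This matters only if the outcome is common and the covariates are prognostic. The protocol's planning figures make preterm birth common. The documents also treat GA as related to outcome: it is a stratification factor (Protocol 5.3), time to delivery is expected to depend on the GA mix (Protocol 8.2.2), and GA enters the mixing probability of the primary model (SAP 7.1.2). At stake is the size of the effect shown as an RR, and whether its interval has its nominal coverage.

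**Working it through.** There is no stated RR to reproduce, so the check is of the method.

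**Inputs from the documents**
- Control risk. Protocol 8.2.1 assumes "approximately 55% of women in the atosiban treatment group will deliver within the 3 weeks of GA at randomization". The latest entry is 33 6/7 weeks (Protocol 4.2), and 33 6/7 weeks + 21 days = 36 6/7. All those births are therefore before 37 weeks, and the implied atosiban preterm risk is at least 0.55. Protocol 8.2.2 also considers 45%, and a further scenario 20 points lower (35%).
- GA mix 1:2:4:8 over the four strata (Protocol 8.2.1). With GA uniform within strata (assumed), the mean is (25 + 2×27 + 4×29.5 + 8×32.5)/15 = 30.5 weeks.
- 300 women with data planned (Protocol 8.2.1); 97 enrolled (SAP section 1).

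**Assumptions, not in the documents**
- Conditional treatment odds ratio 0.26, 0.5 or 0.7; progesterone prevalence 15%.
- Weak covariates: GA log-odds slope 0.1 per week, progesterone odds ratio 1.5. Moderate: 0.25 and 2. Strong: 0.5 and 2.

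**Formula.** Usual conversion: RR = OR / (1 − p0 + p0 × OR), with p0 the crude control risk.

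**Case with no covariates.** The Phase II preterm rates in Protocol 1.2 are 18.7% and 47.2%. The crude RR is 0.187/0.472 = 0.396 and the OR is (0.187/0.813)/(0.472/0.528) = 0.257. Converting, 0.257/(0.528 + 0.472×0.257) = 0.396. The conversion is exact here.

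**With prognostic covariates, p0 = 0.55, conditional OR 0.5.** The conversion gives 0.5/(0.45 + 0.275) = 0.690 whatever the covariates do. The true marginal values come from averaging the logistic model over the GA mix:

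| Covariates | Marginal OR | Marginal RR | Converted RR | Shift |
|---|---|---|---|---|
| None | 0.500 | 0.690 | 0.690 | 0% |
| Weak | 0.507 | 0.696 | 0.690 | −0.9% |
| Moderate | 0.536 | 0.720 | 0.690 | −4.2% |
| Strong | 0.602 | 0.771 | 0.690 | −10.5% |

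Putting the marginal OR into the same formula recovers the marginal RR, for example 0.536/(0.45 + 0.55×0.536) = 0.720. So the whole discrepancy comes from using the conditional OR. In the moderate row a 28% risk reduction is shown as 31%; in the strong row 23% is shown as 31%.

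**Other settings**
- OR 0.26, p0 0.55: −2.1%, −9.7%, −23.5% (weak, moderate, strong).
- OR 0.7, p0 0.55: −0.4%, −1.9%, −4.8%.
- OR 0.5, p0 0.35, strong: 0.705 becomes 0.606 (−14%).
- Baseline risk taken at mean covariates instead of the crude risk: at p0 0.55, OR 0.5, strong, 0.708 against a true 0.771 (overstated); at p0 0.75, OR 0.7, strong, 0.927 against 0.922 (slightly understated).

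**Interval.** The limits of the OR interval were converted in simulated trials. In five settings with OR 0.5, coverage was 91.6% to 97.9% at N = 300 and 94.8% to 98.4% at N = 96. With control risk 0.53 and the most extreme pair tried (treatment log-OR −1.2, GA slope 0.5 per week), it was about 82–85% at N = 300.

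**Standardisation.** Averaging predicted risks from the same model under each treatment, N = 300, p0 0.55, OR 0.5: 0.720 against a true 0.720 (moderate) and 0.768 against 0.771 (strong). The conversion averaged 0.686 and 0.680. Coverage of the standardised interval was about 95%.

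**The case against.** The strongest reply is that the plan does not contain the step being criticised. It writes no formula and names no baseline risk, and the SAP lists the RR without any conversion. A reader might infer that the plan as written necessarily exaggerates benefit. The documents do not support that: with non-prognostic covariates there is no bias, with weak ones it is about 1%, and with a mean-covariate baseline the error can go either way. This stands. It does not remove the point, because deriving the RR from the adjusted odds ratio is the only instruction in either document and nothing withdraws it.

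A reader might also infer that the neonatal composite is common and so equally affected. Neither document gives a composite rate; only preterm birth can be bounded.

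Nor is coverage near 82% a fair summary. It arises only in the extreme setting at N = 300. A GA slope of 0.5 per week implies an odds ratio of about 138 across the entry range (exp(0.5 × 9.86)).

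The trial stopped at 97 women. With treatment log-OR −0.7 and GA slope 0.25 per week, the median converted interval at that size was 0.36 to 1.07, against a shift from 0.705 to 0.674. Counts and percentages per arm are also reported, so a crude RR can be checked from the same table. All of this limits the practical harm.

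**Conclusion.** The point holds as a reporting weakness. The RR and its interval have no specified method beyond derivation from a conditional odds ratio, and the usual way of carrying that out moves the RR away from 1 when GA or progesterone use predicts the outcome. The direction is certain only for the crude-control-risk conversion under a common conditional odds ratio. The size, roughly 1% to 10% at an odds ratio of 0.5 and control risk 0.55, rests on assumed covariate effects. Converted limits have no guaranteed 95% coverage, though they mostly fell between 92% and 98%. The hypothesis tests, p-values and sequential order come from the logistic model or, for length of stay, from a separate analysis, and do not change. At 97 women the bias is usually small relative to sampling error; the exception is strong covariates with a strong treatment effect.

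**What to change.** Replace the conversion sentence in Protocol 8.3.5.1.2, and state the same method in SAP 8.1.2 so that SAP 8.1.3 and 8.2.4.1 inherit it:

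- From the fitted logistic model, predict each subject's risk under retosiban and under atosiban, and average each over the ITT population (for ICU or NICU admission, over the Neonatal Safety Population used for that display).
- Report the ratio as the RR, and the difference as the risk difference, with delta-method 95% CIs (log scale for the RR). Keep the adjusted odds ratio, its CI and the p-value as they are.
- For the multiply imputed composite (SAP 11.7.2), compute the standardised log RR and its delta-method standard error in each imputed dataset, pool by Rubin's rules and back-transform, alongside the existing log odds ratio.

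The cost is a small amount of extra programming, somewhat more for the imputed composite because it needs its own variance and pooling step. No new data are needed and no test changes.
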